Any patient who withdraws from the study for treatment related toxicity prior to being evaluated for response will be considered a nonresponder. Patients who drop out of the study for other reasons prior to being assessed for response will be considered non-evaluable and may be replaced.

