4.3.1 Number of Patients

A sufficient number of patients will be screened in order to obtain up to 128 eligible and evaluable patients for dosing.

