11.3 Analysis Populations

The intent-to-treat (ITT) patient population includes all patients randomized/enrolled to receive study drug regardless of whether they actually received study drug and regardless of whether evidence is found indicating they failed to meet study inclusion/exclusion criteria or had other protocol violations.

When the ITT patient population is analyzed, patients are grouped according to their randomized/assigned treatment regardless of actual treatment received.

The safety patient population is the subset of ITT patients who received at least one dose of study drug. When the safety patient population is analyzed, patients are grouped according to actual treatment received.

The per-protocol patient population is the subset of safety patients who either (a) have at least one response assessment on study, or (b) die prior to their first scheduled response assessment. However, patients are excluded from the per-protocol patient population if they have an important protocol deviation, such as when evidence is found indicating they failed to meet any study inclusion/exclusion criterion. When the per-protocol patient population is analyzed, patients are grouped according to actual treatment received.

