11.4.2 Efficacy Analyses

Efficacy analyses will be conducted on data collected from patients enrolled in Stage 1 and Stage 2. Patients enrolled in the safety lead-in cohort will not be included in the efficacy analyses since they will receive a lower dose of alvocidib than the patients enrolled in Stage 1 and Stage 2. Response to treatment will be determined using the remission definitions detailed in the 2017 European LeukemiaNet Recommendations in AML [47] (see [Appendix E](#)).

Descriptive statistics will be calculated within and across treatment arms for all efficacy endpoints (see in [Section 7.2](#) for a description of the primary and secondary efficacy endpoints).

The numbers of Combined complete remissions (ie, patients with a best response of CR or CRi), Complete remissions, Composite complete remissions (patients with a best response of CR, CRi, or CRh), and Combined responses (patients with a best response of CR, CRi, CRh, MLFS, or PR) will be summarized by observed response rates and estimated 95% CIs.

Kaplan-Meier time-to-event analyses will be conducted on overall survival, progression-free survival and duration of composite CR. Mortality (all causes) at 30 and 60 days after the last treatment will also be calculated.

Additional exploratory analyses may be performed to assist the sponsor in planning future studies.

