APPENDIX G – ADDITIONAL STATISTICAL INFORMATION

The following SAS programming statements and SAS output were used to confirm the statistical properties of the study design.

```
proc seqdesign boundaryscale=pvalue;
  design
    alpha=0.025
    alt=upper
    beta=0.2
    info=cum(2 5)
    method=errspend(1 10)
    nstages=2
    stop=both;
  samplesize model=onesamplefreq(nullprop=0.1 prop=0.2);
run;
```

DESIGN INFORMATION	
Statistic Distribution	Normal
Boundary Scale	p-Value
Alternative Hypothesis	Upper
Early Stop	Accept/Reject Null
Method	Error Spending
Boundary Key	Both
Alternative Reference	0.1
Number of Stages	2
Alpha	0.025
Beta	0.2
Power	0.8
Max Information (Percent of Fixed Sample)	101.6893
Max Information	798.1471
Null Ref ASN (Percent of Fixed Sample)	77.45185
Alt Ref ASN (Percent of Fixed Sample)	91.0849

METHOD INFORMATION

Boundary	Method	Alpha	Beta	Alternative Reference	Drift
Upper Alpha	Error Spending	0.02500	.	0.1	2.82515
Upper Beta	Error Spending	.	0.20000	0.1	2.82515

BOUNDARY INFORMATION (p-Value Scale); Null Reference = 0

Stage_	Information Level			Alternative	Boundary Values	
				Reference	Upper	
	Proportion	Actual	N	Upper	Beta	Alpha
1	0.4000	319.2588	51.08141	1.78678	0.60525	0.00250
2	1.0000	798.1471	127.7035	2.82515	0.02407	0.02407

SAMPLE SIZE SUMMARY

Test	One-Sample Proportion
Null Proportion	0.1
Proportion	0.2
Test Statistic	Z for Proportion
Reference Proportion	Alt Ref
Max Sample Size	127.7035
Expected Sample Size (Null Ref)	97.26562
Expected Sample Size (Alt Ref)	114.3863

SAMPLE SIZES (N) One-Sample Z Test for Proportion

Stage_	Fractional N		Ceiling N	
	N	Information	N	Information
1	51.08	319.3	52	325.0
2	127.70	798.1	128	800.0

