The sponsor may elect to close enrollment in Stage 1 once the minimum response threshold has been met in Stage 1 (as defined in the Study Design), and the sponsor has sufficient information to select the recommended alvocidib-based treatment arm for Stage 2. The recommended alvocidib-based treatment will be determined subjectively by comparing the response rates, relative safety, and the risk-benefit ratio of the two Stage 1 treatment arms.

2. Stage 2

Current Status: As of November 17, 2020, zero patients were enrolled in Stage 2.

Planned: Determination of the recommended alvocidib-based treatment arm for Stage 2 will be subjective, comparing the response rates, relative safety, and the risk-benefit ratio of the two Stage 1 treatment arms. An additional 76 patients will be enrolled into the treatment arm selected for Stage 2 for a total of 102 patients (26 and 76 from Stages 1 and 2, respectively). The combined CR rate (primary endpoint) will be tested at the end of Stage 2, with statistical significance declared if the one-sided p-value is <0.02407.

Any patient who withdraws from the study for treatment-related toxicity prior to being evaluated for response will be considered a non-responder. Patients who drop out of the study for other reasons prior to being assessed for response will be considered non-evaluable and may be replaced.

Study treatments:

Alvocidib + Low-dose cytarabine treatment will be given every 28 days.

Alvocidib treatment will be given every 28 days

Number of patients planned: It was planned that up to 6 evaluable patients will be enrolled into the Safety Lead-In Cohort, 52 evaluable patients in Stage 1, and 76 patients into Stage 2. Thus, up to 134 evaluable patients may be enrolled in the study.

Study Duration: The study was expected to take 18 months to enroll approximately 134 evaluable patients and an additional 2 years for follow up.

As of the study termination date of November 17, 2020; 11 patients have enrolled into this study.

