5. RANDOMIZATION, BLINDING, AND REPLACEMENT OF PATIENTS

This study follows a randomized, two-stage design. During the Lead-in Cohort and Stage 1, patients will be randomized 1:1 to receive either ALDAC or ALV:

- ALDAC – Alvocidib plus Low Dose Ara-C (cytarabine)
- ALV – ALVocidib

Randomization to treatment arm will be stratified by response to initial induction therapy with venetoclax in combination with azacytidine or decitabine:

- Refractory: failed to achieve a CR/CRi or achieved a CR/CRi with duration <90 days
- Relapsed: reoccurrence of disease following a CR/CRi with duration \geq 90 days

Although this study is randomized, it is unblinded. IQVIA (data management vendor) was responsible for the randomization schedule and implementation into the EDC system.

Patients who are lost to follow-up or withdraw consent for study participation prior to administration of study drug may be replaced, at sponsor's discretion.

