9.5.3 Other Situations

For patients who are withdrawn from the study prior to study completion, all data compiled up to the point of discontinuation will be used for analysis. All withdrawals will be included in all analyses up to the time of withdrawal.

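### As planned, patients who leave unassessed for reasons other than treatment-related toxicity are non-evaluable and replaceable even if dosed, and no analysis set is named for the 10% test or the Stage 1 gate

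*Protocol*

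**What the plan says.** **The rule.** Protocol 4.1, the synopsis (Study Design) and SAP section 2 give it in the same terms. Withdrawal for treatment-related toxicity before evaluation is non-response. For the rest, "Patients who drop out of the study for other reasons prior to being assessed for response will be considered non-evaluable and may be replaced".

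**Targets.** Protocol 4.3.1: "A sufficient number of patients will be screened in order to obtain up to 128 eligible and evaluable patients for dosing". SAP section 2 plans "52 evaluable patients in Stage 1, and 76 patients into Stage 2". The synopsis also counts planned enrollment in evaluable patients.

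**Text that pulls the other way.**
- SAP section 5 covers patients who are lost to follow-up or who "withdraw consent for study participation prior to administration of study drug may be replaced". That is narrower than SAP section 2.
- SAP 9.5.3: "All withdrawals will be included in all analyses up to the time of withdrawal".
- Protocol 11.4.2: "Efficacy analyses will be conducted on data collected from patients enrolled in Stage 1 and Stage 2". This names stages, not an analysis set.
- The per-protocol set (Protocol 11.3, repeated in SAP section 6) keeps patients who "b) die prior to their first scheduled response assessment". Protocol 4.1 does not mention such deaths.

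**Analysis sets.** Protocol 11.3 and SAP section 6 define ITT, safety and per-protocol sets. Neither assigns one to the final test or to the Stage 1 gate.

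**After closure.** SAP section 1 records 11 enrolled patients and no inferential efficacy analysis. SAP section 6 uses the safety population for all summary tables because of the study status. SAP section 11 keeps a response class for patients not evaluated or missing.

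**The concern.** The planned test compares one observed rate with a fixed 10%, so there is no control arm in which the same exclusions would offset. The first scheduled response marrow is at Day 28 of Cycle 1. A dosed patient who leaves before then, for example by choice or because of decline, can fall under the replacement rule. If such patients would have responded less often than those assessed, removing and replacing them raises the observed rate, with the gate and the final test both tilted towards success. Because no analysis set is named, two statisticians could follow the documents faithfully and use different denominators, and near the gate that could decide whether Stage 2 opens.

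**Working it through.** **1. The plan's own figures.** Inputs from Protocol 11.2 and Appendix G: null 10%, alternative 20%, one-sided alpha 0.025, power 0.80, information fraction 0.40.
- Fixed N = ((1.960 + 0.842)/0.10)² × 0.2 × 0.8 = 125.58.
- Times Appendix G's inflation factor 1.016893 = 127.70, rounded up to 128.
- Times 0.4 = 51.08, rounded up to 52.
- The boundaries recompute to p = 0.60525 (gate) and p = 0.02407 (final).

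The stated design reproduces. The variance used is that at 20%.

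**2. The gate.** At 5/52 the one-sided p is 0.6046 (exact) or 0.537 (Z, null variance), and both pass. At 4/52 it is 0.777 or 0.710, and both fail. So more than 4 of 52 is the right count on either form. Now keep the replaced patients in the denominator, still with 5 responders:
- one extra patient, 5/53: exact p = 0.622, fails;
- four extra, 5/56: null-variance Z p = 0.6054, fails.

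**3. Final cut-offs.** Appendix G is headed "One-Sample Z Test for Proportion" but does not settle the form of the final test, so three forms are shown. Up to 128 patients are to be evaluated for efficacy, while the selected arm totals 102 (26 + 76), so both sizes are shown. Smallest number of responders giving p < 0.02407:

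| Test | N=128 | N=102 |
|---|---|---|
| Z, null variance | 20 | 17 |
| Exact | 21 | 18 |
| Z, variance at 20% | 22 | 19 |

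**4. Effect of exclusion.** Let d be the fraction unassessed and r the response rate of unassessed relative to assessed patients. The documents give neither, so both are assumed. If the true rate in all treated patients is 10%, the rate among evaluable patients is 0.10/(1 − d + r·d). At d = 10% this is 0.10/0.90 = 11.1% for r = 0, 0.10/0.95 = 10.5% for r = 0.5, and 10% for r = 1.

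Probability of rejecting at the final look (binomial tail, gate ignored):

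| N, test | d=0 | d=10%, r=0 | d=10%, r=0.5 |
|---|---|---|---|
| 128, exact | 1.6% | 4.4% | 2.7% |
| 128, Z null variance | 3.0% | 7.4% | 4.7% |
| 128, Z variance at 20% | 0.8% | 2.5% | 1.5% |
| 102, exact | 1.2% | 3.2% | 2.0% |
| 102, Z null variance | 2.5% | 5.8% | 3.8% |
| 102, Z variance at 20% | 0.6% | 1.7% | 1.0% |

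With r = 1 each row stays at its d = 0 value. Including the gate changes little: for the exact test at N=128, 1.58% becomes 4.36% at r = 0.

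The chance of passing the gate at a true 10% is 60.5% at d = 0. At d = 10% it is 69.9% (r = 0) or 65.1% (r = 0.5).

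**The case against.** A reader might infer that the plan drops dosed patients, early deaths included, from the denominator and so inflates the type I error. The documents do not support that much.

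- **Exclusion is implied, not stated.** It follows from non-evaluable status, replacement and evaluable-patient targets. No section gives the denominator, and SAP sections 5 and 9.5.3 and Protocol 11.4.2 lean towards inclusion. This stands: the defect is ambiguity and inconsistency.
- **Early deaths are not shown to be excluded.** The only text that addresses death before the first assessment keeps those patients, even in the per-protocol set. This stands, and it matters because zero response is most plausible for early deaths.
- **The inflation depends on what 10% means.** The documents do not say whether the null is a rate in all treated or in evaluable patients. If evaluable, nothing is inflated. This stands.
- **The size depends on assumptions.** d is not given, and response sampling at End of Treatment (Protocol 5.4) may keep it small. Under the variance form Appendix G uses for sample size, 10% unassessed with no responders only brings N=128 to about the nominal 2.5%, and N=102 stays below it.
- **Nothing inferential remains.** The trial closed early, and SAP 7.1 says no formal efficacy interim analysis is planned.

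What survives is that the replacement rule has no limit to undosed patients, SAP sections 2 and 5 conflict, and no analysis set carries the test or the gate. The safety-population note does not fill that gap, because it is tied to closure and covers summary tables only.

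**Conclusion.** The point holds for the design as planned, at minor severity. The documents imply, but do not state, that patients unassessed for reasons other than treatment-related toxicity leave the CR/CRi denominator. They contradict each other on who may be replaced and leave the primary set unnamed.

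The test is anti-conservative only if the 10% null is a rate in all treated patients and the unassessed respond less often than the assessed. With an assumed 10% unassessed and no response among them, false rejection is roughly two and a half to three times its value without exclusions. Whether that exceeds 2.5% depends on the form of the test and on whether N is 128 or 102. At half the response rate the rise is smaller, and at equal response it is nil.

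No result of this trial is affected: only 4 patients entered Stage 1 and no efficacy test will be run. The closed-trial tables already use the safety population with a class for missing responses.

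**What to change.** **Planned design.**
- In the synopsis, Protocol 4.1 and SAP section 2, name all treated Stage 1 and Stage 2 patients as the primary denominator for both the gate and the final test.
- Count every treated patient without a response assessment, early deaths included, as a non-responder.
- Reconcile those three places with Protocol 11.3 and SAP sections 5 and 9.5.3, so that one replacement rule and one treatment of early deaths remain.
- Report the evaluable-only rate as a sensitivity analysis.
- State that 10% and 20% are rates in all treated patients, or restate the power.

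**Cost.** The observed rate will be lower, and the rule is conservative if some unassessed patients would have responded. At 10% unassessed, a true 10% rate is counted as 9.0% when they respond equally often (0.10 × 0.90). If 20% was meant among evaluable patients, the rate tested becomes 0.20 × 0.90 = 18%. Single-look power at N=128 then falls from 91/87/82% to 79/71/63% for cut-offs 20/21/22.

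**Closed-trial report (optional).** Add one sentence to SAP section 11 saying that response percentages use all dosed patients. SAP 8.4 and section 9 refer to percentages of the data available, while 8.4 also defaults to the population count.

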4.2 Randomization Criteria

This study follows a randomized, two-stage design. During Stage 1, patients will be randomized 1:1 to receive either ALDAC or ALV:

- **ALDAC** – Alvocidib plus Low Dose Ara-C (cytarabine)
- **ALV** – ALVocidib

Randomization to treatment arm will be stratified by response to initial induction therapy with venetoclax in combination with azacytidine or decitabine:

- Refractory: failed to achieve a CR/CRI or achieved a CR/CRI with duration <90 days
- Relapsed: reoccurrence of disease following a CR/CRI with duration ≥ 90 days

The sponsor may elect to close enrollment in Stage 1 once the minimum response threshold has been met in Stage 1 (as defined in the Study Design), and the sponsor has sufficient information to select the **recommended** alvocidib-based treatment arm for Stage 2. The **recommended** alvocidib-based treatment will be determined subjectively by comparing the response rates, relative safety, and the risk-benefit ratio of the two Stage 1 treatment arms.

4.3 Patient Population

Patients enrolled in this study must have refractory or relapsed AML after initial induction therapy with venetoclax in combination with azacytidine or decitabine.

4.3.1 Number of Patients

A sufficient number of patients will be screened in order to obtain up to 128 eligible and evaluable patients for dosing.

4.3.2 Inclusion Criteria

To be eligible for participation in the study, patients must meet all of the following inclusion criteria:

1. Be ≥ 18 years of age
2. Have an established, pathologically confirmed diagnoses of AML by World Health Organization (WHO) criteria excluding acute promyelocytic leukemia (APL-M3) with a bone marrow of $>5\%$ blasts based on histology or flow cytometry

3. Are refractory (ie, failed to achieve a CR/CRI or achieved a CR/CRI with duration <90 days) or have relapsed (reoccurrence of disease following a CR/CRI duration ≥90 days) after initial induction therapy with venetoclax in combination with azacytidine or decitabine (***with or without other investigational agents as part of a clinical trial; requires Medical Monitor review***)
4. Have an Eastern Cooperative Oncology Group (ECOG) performance status (PS) ≤2
5. Have a GFR ≥30 mL/min using the Cockcroft-Gault equation
6. Have an alanine aminotransferase (ALT)/aspartate aminotransferase (AST) level ≤5 times upper limit of normal (ULN)
7. Have a total bilirubin level ≤2.0 mg/dL (unless secondary to Gilbert syndrome, hemolysis, or leukemia)
8. Be infertile or agree to use an adequate method of contraception. Sexually active patients and their partners must use an effective method of contraception associated with a low failure rate prior to study entry, for the duration of study participation, and for at least 3 months (males) and 6 months (females) after the last dose of study drug
9. Be able to comply with the requirements of the entire study
10. Provide written informed consent prior to any study related procedure. (In the event that the patient is re-screened for study participation or a protocol amendment alters the care of an ongoing patient, a new informed consent form must be signed.)

4.3.3 Exclusion Criteria

Patients meeting any one of these exclusion criteria will be prohibited from participating in this study.

1. Received any previous treatment with alvocidib or any other CDK inhibitor or received prior anti-leukemic therapy other than first-line venetoclax in combination with azacytidine or decitabine
2. Require concomitant chemotherapy, radiation therapy, or immunotherapy. Hydroxyurea is allowed up to the evening before starting (but not within 12 hours of starting) treatment on either arm
3. Received an allogeneic stem cell transplant within 60 days of treatment. Subjects who received an allogeneic stem cell transplant must be off all immunosuppressants at the time of study treatment
4. Receiving systemic therapy for graft-versus-host disease

5. Have a peripheral blast count of $>30,000/\text{mm}^3$ (may use hydroxyurea as in #2 above)
6. Received antileukemic therapy within the last **2 weeks or 3-5 half lives of the prior therapy** (with the exception of hydroxyurea or if the patient has definite refractory disease), **whichever is less**. Refractory patients who received therapy within the last **2 weeks** may be eligible with prior approval of the Medical Monitor.
7. Diagnosed with acute promyelocytic leukemia (APL-M3)
8. Have active central nervous system (CNS) leukemia
9. Have evidence of uncontrolled disseminated intravascular coagulation
10. Have an active, uncontrolled infection
11. Have other life-threatening illness
12. Have other active malignancies requiring treatment or diagnosed with other malignancies within the last 6 months, except nonmelanoma skin cancer or cervical intraepithelial neoplasia
13. Have mental deficits and/or psychiatric history that may compromise the ability to give written informed consent or to comply with the study protocol
14. Are pregnant and/or nursing
15. Have received any live vaccine within 14 days prior to first study drug administration

4.4 Study Treatments

4.4.1 Calculation of Dose

The patient's weight will be taken at the beginning of each new treatment cycle to determine whether a $> 10\%$ change in body weight occurred. The dose of ALV or LDAC will remain the same as Cycle 1 for all subsequent treatments unless there has been a $> 10\%$ change in body weight. If there has been a $> 10\%$ change in body weight, the BSA should be recalculated and the dose adjusted accordingly.

4.4.2 Study Drug Administration

Lead-in Cohort, Two Arms (at least 3 patients per arm)

As an additional safety measure given the unique patient population and novel outpatient treatment administration, a lead-in cohort of **approximately** six patients (**at least** three patients in each treatment arm) will be enrolled, treated, and evaluated for DLTs. If a DLT is observed, dose de-escalation will occur as

outlined in [Appendix F](#). Should no additional DLTs be observed during Cycle 1, **Amendment 2 has been approved, and the DSMB has confirmed safety**, randomization *into Stage 1* will commence as outlined in the protocol. However, should an additional DLT be observed at Dose Level 1, a clinical meeting would be scheduled to discuss the utility/futility of continuing the study as currently designed.

If patients treated in the lead-in cohort are still on study when Amendment 2 is approved and the DSMB has confirmed safety, they may be permitted to shift to the higher alvocidib dose regimen, ie, ALV 50 mg/m² IV bolus, per investigator discretion.

Stage 1 Randomized, Two Arms (26 patients per Arm)

Stage 1 of the study is comprised of two arms with study drug administration schedules as follows:

- **ARM 1: Alvocidib plus low-dose cytarabine (ALDAC);** treatment will be given every 28 days
 - **Cycle 1** Day 1: alvocidib 25 mg/m² as a 30-60 minute intravenous (IV) bolus
Cycles 2+ Day 1: alvocidib 50 mg/m² as a 30-60 minute IV bolus
 - Day 2: no treatment
 - Days 3 through 12 (10 days): LDAC, 20 mg/m² by subcutaneous (SC) injection
 - Day 15: alvocidib 50 mg/m² as a 30-60 minute IV bolus
- **ARM 2: Alvocidib (ALV);** treatment will be given every 28 days
 - **Cycle 1** Day 1: alvocidib 25 mg/m² as a 30-60 minute IV bolus
Cycles 2+ Day 1: alvocidib 50 mg/m² as a 30-60 minute IV bolus
 - Days 8 and 15: alvocidib 50 mg/m² as a 30-60 minute IV bolus

The treatment schema is outlined in [Figure 1](#).

Stage 2, Single Arm (76 patients)

Regimen to be selected based on Stage 1 performance.

Additional Cycles of Treatment in Stage 1 and Stage 2

Patients who achieve CR, CRi, CRh, MLFS, PR, or clinical benefit after the first cycle (completion of all doses) may receive additional optional cycles of treatment until disease progression (in the event of toxicities see the recommendations in [Table 3](#), if applicable).

Those who achieve a CR, CRi, CRh, or MLFS (i.e. <5% blasts in bone marrow) **should** not be given **subsequent cycles** until ANC >0.5 and platelets >50. If treatment is delayed >2 weeks for cytopenias, a bone marrow biopsy should be performed to reassess disease status.

Patients not demonstrating evidence of CR, CRi, MLFS, PR, or clinical benefit after 4 cycles of treatment will be considered for removal from the study, although with permission of the Medical Monitor, treatment may continue if clinically indicated (in the event of toxicities see the recommendations in **Table 3**, if applicable).

[figure not shown]

Figure 1: Treatment Schema for Lead-in Cohort and Stage 1

ALDAC=alvocidib plus low-dose cytarabine; LDAC=low-dose cytarabine

* If patients treated in the lead-in cohort are still on study when Amendment 2 is approved and the DSMB has confirmed safety, they may be permitted to shift to the higher alvocidib dose regimen, ie, ALV 50 mg/m² IV bolus, per investigator discretion.

**Alvocidib dose will be 50 mg/m² beginning in Cycles 2+ after completion of the safety lead-in cohort. No dose reductions will be permitted after the lead-in cohort is completed.

